4.0 Treatment Assignment

- 4.1 All patients who meet the eligibility criteria, sign the patient informed consent form, obtain physician consent, and complete baseline assessments will immediately be randomized to one of four treatment arms. Randomization will be determined by means of a computer-generated random number table.
 - 4.1.1 This study will use a block-randomized scheme with block sizes of 8 to ensure an equal distribution among the four arms.
 - 4.1.2 A total enrollment of 72 patients is planned (18 in each treatment arm).
 - 4.1.3 Treatment sequence in the four trial arms will be as follows:

Treatment Arm	Condition
1	Calcitriol 45 µg : Patients will be given 45 µg/week of calcitriol beginning at baseline for a period of 12 weeks.
2	Home-Based Exercise : Patients will be given a progressive walking and resistance band exercise treatment and a daily multivitamin for a period of 12 weeks.
3	Calcitriol 45 µg and Home-Based Exercise : Patients will be given 45 µg/week of calcitriol along with a progressive walking and resistance band exercise treatment for a period of 12 weeks.
4	Usual Care : A daily multivitamin plus standard care monitoring.

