5.5.1.1 The calcitriol 45 μ g pills will be supplied by Roswell Park Cancer Institute and the State University of New York at Buffalo. The pills will be placed in a tamper-proof blister pack. Research subjects will be instructed to take the calcitriol on an empty stomach, 1 to 2 hours prior to or after any meal. Subjects will also be advised to increase their intake of water by 4 cups on the day of taking the pill and the day after. Subjects will take 1 capsule 1 day a week for a duration of 12 weeks. Subjects will be supplied with the full 12 weeks of capsules that will be dispensed by the University of Rochester Medical Center pharmacy.

5.5.1.2

5.5.1.3 The study coordinator will contact each subject on the day she is scheduled to take calcitriol 45 µg as a reminder. The study coordinator will use this opportunity to assess any potential complications or toxicities due to the intervention.

5.5.1.4 Because of improved calcium absorption from the gastrointestinal tract caused by calcitriol, most participants may be maintained on a lower calcium intake. Most patients on calcitriol require only dietary sources of calcium and need no supplementation. Therefore, participants must not take multivitamin or calcium supplementation while on the study medication. In addition, ingestion of large amounts of foods containing dairy products should be avoided. Participants assigned to calcitriol who are routinely taking a multivitamin supplement may continue the supplement as long as the amount of vitamin D in the supplement is not in excess of the RDA (recommended daily allowance) of 400 IU or 10 µg. If they are not taking a multivitamin supplement, they will be asked to not start supplementation while on study.

5.5.2 Toxicity Monitoring:

After the first dose of calcitriol is administered on day 0, the patients will return for blood collection on day 5. On day 5, any patient displaying any grade ≥ 3 toxicity related to the study drug will be removed from the study. The patients will return at 6 weeks and 12 weeks for blood collection. These visits will be coordinated with surgical oncology visits, medical oncology visits, or radiation oncology visits, when possible, to reduce patient burden. Following her appointment, the patient will proceed directly to phlebotomy.

Removal from study: Patients will be removed from the study for any of the following reasons:

1. Any grade ≥ 3 toxicity related to the study drug.

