2. A grade 2 toxicity that persists for more than 2 weeks.
3. Withdrawal of consent.

For any clinically adverse event, the toxicity grading scale established by the FDA will be used. It is as follows:

Grade 1 toxicity (Mild): No interference with activity

Grade 2 toxicity (Moderate): Some interference with activity not requiring medical intervention.

Grade 3 toxicity (Severe): Prevents daily activity and requires medical intervention.

Grade 4 toxicity (Potentially Life Threatening): ER visit or hospitalization.

For hypercalcemia, the FDA toxicity grading scale specific to serum calcium will be used:

Grade 1 toxicity (Mild): 10.3-11.0 mg/dL

Grade 2 toxicity (Moderate): 11.1-11.5 mg/dL

Grade 3 toxicity (Severe): 11.6-12.0 mg/dL

Grade 4 toxicity (Potentially Life Threatening): > 12.0 mg/dL

The FDA toxicity grading scale will be used for determining all adverse events.

In addition to blood safety checks throughout the study, a research coordinator will call each patient at on the day of the week she is scheduled to take calcitriol 45 µg to ensure compliance and assess side effects. The nurse will record any adverse events (AE) and/or serious adverse events (SAE). Any patient who reports an AE or SAE will be scheduled for a clinical visit. In addition, the research coordinator will inquire as to any change in over the counter supplement usage. Reports regarding potential toxicities, patient safety, and outcomes will be submitted to the University of Rochester Medical Center Research Subjects Review Board (RSRB). The potential risks and side effects of calcitriol include:¹⁵⁵

Because calcitriol is the active analog of vitamin D, adverse effects are similar to those found with excessive vitamin D intake. Because of the short biological half-life of calcitriol, elevated serum calcium levels normalize within a few days, much more quickly than with native vitamin D supplementation.

Early signs and symptoms of vitamin D intoxication: Weakness, headache, somnolence, nausea, vomiting, dry mouth, constipation, muscle pain, bone pain, metallic taste, anorexia, abdominal pain, or stomach ache.

Late signs and symptoms of vitamin D intoxication: Polyuria, polydipsia, anorexia, weight loss, nocturia, conjunctivitis, pancreatitis, photophobia, rhinorrhea, pruritus, hyperthermia, decreased libido, elevated BUN,

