Safety Coordinator: The Medical Director of the Cancer Center Clinical Trials Office appoints the Safety Coordinator. The Safety Coordinator monitors adverse event rates utilizing the URCC Clinical Trials database. If any assigned study has had two or more of the same SAEs reported in a month or more than six of the same SAEs in six months, the DSMC will review the summary of SAEs, discuss events with the Study Chair, and conduct a more detailed review with the Study Chair. The Data Safety Monitoring Chair will determine if further action is required.

- 5.5.6 All study drugs will be dispensed and all biological specimens will be collected at the University of Rochester Medical Center.
- 5.5.7 There will be no cost to the patient for the study medication, the pathological tests, blood tests, or bone health tests. All costs will be paid from funds controlled by [name] within the James P. Wilmot

Cancer Center.

5.6 Walking and Progressive Resistance Exercise Arms 2 & 3

- 5.6.1 The Home-Based Walking and Progressive Resistance Exercise Program is designed by an Exercise Scientist certified by the American College of Sports Medicine (ACSM) and is in accordance with the guidelines for exercise testing and prescription as set forth by the ACSM.
- 5.6.2 The Home-Based Walking and Progressive Resistance Exercise Program will follow the guidelines listed below.
 - 5.6.2.1 The Home-Based Walking Prescription will be based on a patient's baseline pedometer assessment. [REDACTED]
 - 5.6.2.2 The Home-Based Progressive Resistance Prescription will be based on a patient's optimal level of challenge. Patients will be instructed on the proper use of resistance bands. [REDACTED]
 - 5.6.2.3 The study coordinator will talk with each patient on a weekly basis by telephone as a reminder to take calcitriol.

He/she will also answer any questions the patient may have regarding the exercise program in order to facilitate proper adherence and compliance to the exercise intervention.

- 5.6.3 All Walking and Progressive Resistance Exercises will be performed off-site from the University of Rochester Cancer Center in a home-based patient-selected environment.

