8.0 Records to be Kept

Procedure	Time Since Randomization			
	0	5 Days	6 Weeks	12 Weeks
Eligibility Interview	+			
Informed Consent	+			
Medical History	+		+	+
Assess Supplement Use	+	+	+	+
Blood CBC Levels	+	+	+	+
Serum 1, 25 OH ₂ D ₃ Levels	+	+	+	+
Bone Biomarkers	+		+	+
On Study Data (Demographics and Clinical Data)	+			+
Phone call reminders	Weekly	Weekly	Weekly	Weekly
Toxicity monitoring	+	+	+	+
Daily Diary	Daily	Daily	Daily	Daily
Functional Assessment of Chronic Illness Therapy (FACIT) (28-item QOL measure & 13-item fatigue subscale)	+			+
Brief Fatigue Inventory (BFI) (Severity of fatigue and level of interference in activities of daily living - 9 items)	+			+
Symptom Inventory (13-item symptom rating scale)	+			+
VO2max Treadmill Test	+			+
Aerobic Center Longitudinal Study Physical Activity Questionnaire (ACLS) (15-item physical activity history measure)	+			+
Pedometer	+			+
Tandem Walk Test (TWT)	+			+
Handgrip Dynamometer	+			+
7-10 Maximum Repetition	+			+
Bioelectrical Impedance Analysis	+			+

8.1 All hardcopy research records will be stored onsite in the University of Rochester Medical Center, in the Behavioral Medicine Unit of the James P. Wilmot Cancer Center. The Cancer Center is secured by electronic key cards. Offices within the Cancer Center are again secured by key and data is kept in locked file cabinets. Electronic research records are stored on the University of Rochester Medical Center's password secured and firewall protected networks. These are the same methods of security used for patient medical records. Human serum samples and biopsy samples are stored in locked freezers, within locked and alarmed laboratories that are accessible by key codes and electronic card swipes. All study data will be kept for a period of 10 years after the study and all reports and publications are complete.

8.2 All data (information, human blood samples, and human tissue samples) collected for the current study will be used in post hoc analyses as appropriate. No blood or biopsy samples will be banked. The patient is provided the opportunity to be contacted for future research studies in the informed consent. The patient's individual research record will not be shared with their treating physician, unless they provide consent or the patient's treating physician is a study physician, in

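### Weekly side-effect and supplement questions are written only for the calcitriol arms, so symptomatic adverse events may be found more often there than in Arms 2 and 4

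*Combined protocol and SAP*

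**What the plan says.** **Arms 1 and 3.** Section 5.5 is headed for these two arms. In 5.5.1.3 the coordinator contacts each woman on her dosing day as a reminder, and "The study coordinator will use this opportunity to assess any potential complications or toxicities due to the intervention". Section 5.5.2 repeats this: "a research coordinator will call each patient at on the day of the week she is scheduled to take calcitriol", and the purpose is "to ensure compliance and assess side effects". The same paragraph has the caller ask about changes in over-the-counter supplements, and adds: "Any patient who reports an AE or SAE will be scheduled for a clinical visit".

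**Arms 2 and 3.** Under 5.6.2.3 the coordinator will "talk with each patient on a weekly basis by telephone as a reminder to take calcitriol" and will answer questions about the exercise program. No inquiry about side effects is stated. Arm 2 receives a multivitamin and exercise, not calcitriol (4.1.3).

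**Arm 4.** Section 4.1.3 gives: "A daily multivitamin plus standard care monitoring". Section 5.8 describes the multivitamin and says nothing about calls or event questions.

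**All patients.** The Section 8.0 table has a row "Phone call reminders" marked weekly in every column. It also has rows for toxicity monitoring and supplement use at baseline, day 5, week 6 and week 12. None of these rows is limited to an arm. Section 5.4.1 sets blood sampling at the same four times, again without an arm limit.

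**The concern.** Section 1.2 makes safe participation in high-dose calcitriol a question for this pilot, and Section 5.5.5 has toxicities reviewed for each treatment arm. A by-arm listing can be read as a comparison only if events are sought in the same way in every arm.

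The early symptoms listed in 5.5.2 include weakness, headache, nausea, constipation and muscle pain. Women in any arm may have these, so the number recorded depends partly on how often someone asks. If the weekly question is put only to women on calcitriol, calcitriol can look less tolerable than it is, and Arms 2 and 4 lose value as a reference. The effect can build on itself, because each reported event leads to a clinical visit at which more may be found.

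Supplement changes have the same problem on a smaller scale. They would be asked about weekly on calcitriol but only at the scheduled visits elsewhere, although Arm 4 women may continue calcium (5.8).

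**Working it through.** The plan states no adverse-event rate, detection rate or safety sample size, so there is no figure to reproduce. The check is a side-by-side reading and a count of contacts.

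**1. Who is asked what**

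| Source | Arm 1 | Arm 2 | Arm 3 | Arm 4 |
|---|---|---|---|---|
| 5.5.1.3, 5.5.2: weekly call with side-effect questions | yes | has no dosing day | yes | has no dosing day |
| 5.6.2.3: weekly call, reminder and exercise help | not covered | yes, no event questions stated | yes, no event questions stated | not covered |
| 4.1.3, 5.8: arm description | – | – | – | no call described |
| 8.0: weekly reminder calls | arm not stated | arm not stated | arm not stated | arm not stated |
| 8.0: toxicity monitoring; 5.4.1: blood draws | all four times | all four times | all four times | all four times |

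**2. Contacts after baseline at which events are sought**

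- Common visits: day 5, week 6, week 12 = 3.
- Calls in Arms 1 and 3: 12 weekly doses give 12 calls. The first dose is on day 0, so if that call is not counted as follow-up there are 11.
- Arm sections read literally: 12 + 3 = 15 (or 11 + 3 = 14) in Arms 1 and 3, against 3 in Arms 2 and 4.
- If the Section 8.0 call row covers every arm and carries the same questions: 15 against 15.

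**3. Scale, by illustration only**

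Suppose the same true proportion p of women has a symptomatic event in every arm. Weekly calls plus visits capture a share c1 of these women, and visits alone capture c2. The recorded proportions are p × c1 and p × c2, and the false gap is p × (c1 − c2). All values of p, c1 and c2 below are assumptions.

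| p | c1 | c2 | Recorded, Arms 1 and 3 | Recorded, Arms 2 and 4 | Gap (points) |
|---|---|---|---|---|---|
| 20% | 90% | 70% | 18% | 14% | 4 |
| 20% | 90% | 50% | 18% | 10% | 8 |
| 30% | 100% | 75% | 30% | 22.5% | 7.5 |
| 30% | 100% | 50% | 30% | 15% | 15 |
| 50% | 100% | 75% | 50% | 37.5% | 12.5 |
| 50% | 100% | 50% | 50% | 25% | 25 |
| 70% | 100% | 75% | 70% | 52.5% | 17.5 |
| 70% | 100% | 50% | 70% | 35% | 35 |

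With 18 women per arm (4.1.2), each pair of arms has 36. The gap then runs from 36 × 0.04 = 1.4 women to 36 × 0.35 = 12.6 women, and it is zero if c1 = c2. The result follows entirely from the assumed values.

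**The case against.** The strongest reply is that the text is loosely drafted and does not set up an unequal design.

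- The 5.5.2 sentence speaks of each patient, and Section 8.0 lists weekly calls for everyone.
- The heading of 5.5 is a weak guide to scope, because the section also holds provisions for the whole trial, such as event reporting and the monitoring plan.
- Section 5.6.2.3 gives a calcitriol reminder to an arm that takes none, and 5.3.2 has calcitriol instructions reviewed with all patients.
- Section 8.0 also gives every patient a symptom inventory at baseline and week 12.

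Most of this stands. It means that Arms 2 and 4 are left unclear, not shut out. It does not settle the matter, because the only written side-effect call is anchored to a day that women in Arms 2 and 4 do not have, and the Section 8.0 row mentions reminders only. Staff following the arm sections would put the question in Arms 1 and 3 alone. A symptom inventory at two times does not replace weekly event recording.

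Some stronger readings are tempting but not supported:

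- **That exercise, too, is watched more closely than usual care.** For stated event questions, Arm 2 is in the same position as Arm 4.
- **That hypercalcemia would be over-detected on calcitriol.** As written, blood is drawn on one schedule in all arms.
- **That a formal safety comparison is invalid.** Section 7 plans no between-arm test of events; the by-arm review in 5.5.5 is descriptive.
- **That the NTx and BAP results are biased through extra attention or unequal removals.** These are serum markers, Arm 2 is called weekly on any reading, and no removal rate is given.

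**Conclusion.** The point holds in a limited form. Weekly side-effect and supplement questions are written only for Arms 1 and 3. Arm 2's call has no stated event inquiry, Arm 4 has no call described, and Section 8.0 does not resolve the difference. Followed literally, symptomatic events may be found more often on calcitriol than in Arms 2 and 4, and the by-arm toxicity review would be biased in that direction.

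A reader might infer that events will certainly be over-counted on calcitriol, or by a known amount. The documents support neither. The contact count of 14 or 15 against 3 depends on the literal reading, and it becomes equal if Section 8.0 was meant to give every arm the same questions. The size of any bias cannot be derived, and the 4 to 35 point range above is illustrative. The primary analyses are not called into question. It is still worth correcting, because safety is a stated purpose and the correction is cheap.

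**What to change.** Reconcile 5.5.2, 5.6.2.3, 5.8 and the Section 8.0 call row so that:

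- all four arms receive the weekly call;
- every call opens with the same scripted adverse-event and supplement questions;
- arm-specific prompts on compliance or exercise come only after those questions;
- the Arm 2 call is no longer described as a calcitriol reminder.

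The call can stay on the dosing day in Arms 1 and 3, with any consistent weekly day in Arms 2 and 4. A common weekday is not needed.

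If the calls are not extended, state that symptomatic events will be compared between arms only as found at the day 5, week 6 and week 12 visits. Events found by telephone would then be listed separately.

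**Cost.** Arm 4 needs about 18 × 12 = 216 short calls, which the Section 8.0 row already implies. Arm 2 is already called weekly and needs only a few added questions. Since no blinding is described, a common script makes the asking equal but does not remove differences in how women who know their arm report symptoms.

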5.5.3 Adverse Events

5.5.3.1 An **adverse event (AE)** is any untoward medical occurrence in a patient administered a pharmaceutical product, which does not necessarily have a causal relationship with the treatment. An adverse event can be any unfavorable and unintended sign (eg, including an abnormal laboratory finding), symptom, or disease temporally associated with the use of the drug, whether or not it is considered to be drug related. This includes any newly occurring event or previous condition that has increased in severity or frequency since the administration of drug.

5.5.3.2 A **serious adverse event (SAE)** is any adverse event, occurring at any dose and regardless of causality that:

- Results in **death**.
- Is **life-threatening**. Life-threatening means that the patient was at immediate risk of death from the reaction as it occurred, i.e., it does not include a reaction which hypothetically might have caused death had it occurred in a more severe form.
- Requires inpatient **hospitalization or prolongation of existing hospitalization**. Hospitalization admissions and/or surgical operations scheduled to occur during the study period, but planned prior to study entry are not considered AEs if the illness or disease existed before the patient was enrolled in the trial, provided that it did not deteriorate in an unexpected manner during the trial (eg, surgery performed earlier than planned).
- Results in **persistent or significant disability/incapacity**. Disability is defined as a substantial disruption of a persons' ability to conduct normal life functions.
- Is a congenital anomaly/birth defect.
- Is an **important medical event**. An important medical event is an event that may not result in death, be life-threatening, or require hospitalization but may be considered an SAE when, based upon appropriate medical judgment, it may jeopardize the patient or subject and may require medical or surgical intervention to prevent

one of the outcomes listed in the definitions for SAEs. Examples of such medical events include allergic bronchospasm requiring intensive treatment in an emergency room or at home, blood dyscrasias or convulsions that do not result in inpatient hospitalization, or the development of drug dependency or drug abuse.

5.5.3.3 An **unexpected adverse event** is any drug experience, the specificity or severity of which is not consistent with the risk information described in the investigators brochure or general investigational plan (see section 5.91). Unexpected as used in this definition refers to an adverse drug event that has not been previously observed rather than from the perspective of such experience not having been anticipated from the pharmacological properties of the drug.

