5.4 Physiological and Psychological Assessments

- 5.4.1 Blood sampling at four time points (baseline, day 5, week 6, and week 12) will be done to estimate bone resorption and formation and as a safety check for hypercalcemia. Measures of bone pathology will be performed through the Associated Regional and University Pathologists (ARUP) Laboratories. Pre and post-intervention tests for Cross-linked N-teleopeptide of type I collagen (NTx), a specific indicator of bone resorption will be performed. In addition, pre and post-intervention tests for bone-specific alkaline phosphatase (BAP), an indication of bone formation, will be performed.
- 5.4.2 The blood draws for estimation of NTx and BAP will use 2 red top tubes for serum.
- 5.4.3 All blood draws will occur in the General Clinical Research Center (GCRC) and the blood will be drawn by research personnel in the GCRC. The time of day will be noted, with future assessments at approximately the same time of day during post-testing and follow-up.
- 5.4.4 All patients will be given a measure of physical activity (Aerobics Center Longitudinal Physical Activity Questionnaire (ACLS)), fatigue

(Functional Assessment of Chronic Illness Therapy Fatigue Subscale (FACIT-F); Brief Fatigue Inventory (BFI); Multidimensional Fatigue Symptom Inventory (MFSI)), QOL (Functional Assessment of Chronic Illness Therapy with Fatigue (FACIT-F)), to complete at home at the appropriate times (i.e. during baseline and post-testing). (Note: Pilot use of the questionnaire packet indicates an average completion time of ≤ 30 minutes).

[figure not shown]
5.4.5 All patients will be evaluated on aerobic capacity (VO₂max Treadmill Test), muscular strength (handgrip dynamometry, 7-10 repetition maximum test), gait (tandem walk test), and skeletal muscle mass (bioelectrical impedance). All physiological fitness testing will be administered according to the Guidelines for Exercise Testing and Prescription (GETP) as outlined by the American College of Sports Medicine (ACSM).

5.5 Calcitriol 45 μ g Arms 1 & 3

5.5.1 The calcitriol 45 μ g arms 1 & 3 will follow the guidelines listed below:

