5.7 Commencement of a low to moderate walking and progressive resistance exercise program is not associated with any severe side effects and risks are minimal for individuals with no cardiopulmonary, orthopedic, or age-identified high risk factors as determined by the patient's treating physician (or designee). The chance of a cardiac event is rare once coronary disease has been excluded with reasonable certainty. Approximately 1 death per 15,000-20,000 healthy men per year occurs during jogging; this risk is much lower in women. A transient increase in blood pressure may occur with all types of exercise. Although unlikely, the risks involved in a low to moderate walking and progressive resistance exercise program are musculoskeletal—possibly mild muscle soreness, a muscle strain, or related injuries such as tripping. Overall, the risk level for participation in a low to moderate Home-Based Walking and Progressive Resistance program is minimal. Risks associated with a 6-minute walk test are similar to participation in a low to moderate walking exercise program and are minimal for individuals with no cardiopulmonary, orthopedic, or age-identified high risk factors as determined by the patient's doctor. 7-10 Repetition maximum tests for strength may cause minor stiffness and/or tenderness in muscles for a few days following testing. The nature of these assessments will require a level of exertion causing temporary changes such as an increase in heart rate and blood pressure, both of which are normal responses to moderate exercise. There is a small risk of irritation to the skin from the electrodes used for the BIA analysis. Lying under the canopy for resting metabolic testing creates a risk for some subjects to feel anxious or claustrophobic. Every effort will be made to minimize the risks for all study procedures through the approval of the treating physician to enter the study, supervision of all testing and exercise prescription by an American College of Sports Medicine certified Health and Fitness Instructor or a physician (or physician's designee) when necessary according to American College of Sports Medicine Guidelines, the use of standardized guidelines for exercise testing and prescription provided by the American College of Sports Medicine and resting metabolic rate testing and bioelectrical impedance analysis. Regarding the risks for resting metabolic testing, if patients feel claustrophobic during the resting metabolic test it will be stopped. Electrodes will be removed

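### The adverse-event definition is worded for a drug, so events at baseline fitness testing fall outside it and events in the two arms without calcitriol are not clearly covered

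*Combined protocol and SAP*

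**What the plan says.** Section 5.5.3.1 defines an adverse event as "any untoward medical occurrence in a patient administered a pharmaceutical product, which does not necessarily have a causal relationship with the treatment". It extends this to signs, symptoms or disease "temporally associated with the use of the drug, whether or not it is considered to be drug related", and to any "newly occurring event or previous condition that has increased in severity or frequency since the administration of drug".

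The two related definitions follow the same line. Under 5.5.3.2 a serious adverse event "is any adverse event, occurring at any dose and regardless of causality that" meets one of the listed criteria. Section 5.5.3.3 ties the unexpected kind to the drug as well: it "is any drug experience, the specificity or severity of which is not consistent with the risk information described in the investigators brochure".

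All three stand within section 5.5, which is headed for the calcitriol arms and opens (5.5.1) by saying that "arms 1 & 3 will follow the guidelines listed below". In 5.5.2, the telephone call at which side effects are assessed is made on the day the woman is due to take calcitriol.

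Section 5.7 foresees harms that do not come from a drug. It says that "the risks involved in a low to moderate walking and progressive resistance exercise program are musculoskeletal", giving soreness, strain and tripping injuries as examples. It also mentions stiffness after the repetition-maximum tests, a passing rise in blood pressure and, rarely, cardiac events. Sections 5.6 to 5.8 contain no definition, collection procedure or reporting rule for such events in their visible text. Parts of 5.6.2.1 and 5.6.2.2 are redacted.

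**The concern.** Exercise is one of the two interventions under test, and arm 2 receives it without calcitriol. A pilot that is meant to inform a later study should be able to say what harm the exercise programme and the fitness tests caused. That requires the same events to be captured by the same rule in every arm and from the first procedure.

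A definition tied to drug administration does not secure this. Site staff who follow it to the letter could record a muscle strain in one exercise arm and not in the other, and could leave out an injury on the baseline treadmill altogether. A simple tabulation of adverse events by arm would then partly reflect the definition.

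**Working it through.** The plan gives no figure to reproduce. The check is to apply the definition to each arm and each period.

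**Inputs**
- Arms (4.1.3): arm 1 calcitriol; arm 2 exercise plus a daily multivitamin; arm 3 calcitriol plus exercise; arm 4 usual care plus a daily multivitamin.
- Planned numbers (4.1.2 and 7.2.1): 72 women, 18 per arm. Section 1.6 gives 54 instead; the shares below depend only on equal allocation.
- Timing: baseline assessments are finished before randomisation (4.1). They include the treadmill and repetition-maximum tests (5.3.1). The first calcitriol dose is on day 0 (5.5.2). The tests are repeated at 12 weeks (schedule in 8.0).
- Nature of the multivitamin: 5.8.1, written for arm 4, calls it a supplement. No section says whether it is a pharmaceutical product for the purposes of 5.5.3.

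**The definition applied literally**

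| Period | Arms 1 and 3 | Arms 2 and 4 |
|---|---|---|
| Baseline testing | Outside: no product yet given | Outside: no product yet given |
| From first study product to week 12 | Covered, whatever the cause | Covered only if the multivitamin counts |
| Week-12 testing | Covered | Covered only if the multivitamin counts |

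**Serious and unexpected events.** A serious event must first be an adverse event, so it takes on the same limits. An unexpected event is a drug experience judged against the drug's risk information, a standard that does not fit an exercise injury in any arm.

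**Arms 2 and 3 compared.** The definition asks for no causal link. A strain from the resistance bands in arm 3 after the first capsule is therefore an adverse event. The same strain in arm 2 is one only on the wider reading of the multivitamin. Enquiry differs too. The side-effect call in 5.5.2 follows the calcitriol day, which arm 2 does not have. The weekly call in 5.6.2.3 is described as a calcitriol reminder and a chance to answer exercise questions, with no stated enquiry about adverse events.

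**Head count**
- Baseline testing outside the definition: 72 of 72 women.
- Arms without calcitriol: 18 + 18 = 36 of 72 (50%).
- Exercise without calcitriol: 18 of 72 (25%), or 18 of the 36 women in arms 2 and 3 (50%).

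**The case against.** The best reply is that the plan as a whole intends to monitor every arm, and that placement within 5.5 proves little, because that section also holds trial-wide text.
- 5.5.4 requires reports of serious events linked to the study, from the time a woman is on study until 14 days after she leaves it. It does not mention dosing.
- 5.5.5 provides for review by treatment arm.
- 5.5.2 applies its grading scale to all adverse events, and the general scale rests on interference with activity, so it can grade a strain.
- The schedule in 8.0 marks toxicity monitoring at 0, 5 days, 6 weeks and 12 weeks, and weekly calls, with no restriction by arm.
- Arm 2 takes a tablet supplied by the study, and 5.5.3.1 speaks of a pharmaceutical product, not of calcitriol.

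Most of this stands, and it limits the point. A reader might infer that arm 2 is definitely excluded. The documents support only that exclusion is the natural literal reading of an unclear text. A reader might also infer that a fracture or cardiac event in arm 2 would go unreported; 5.5.4 makes that too strong, although it uses the term defined in 5.5.3.2. Nor is all fitness testing outside the definition: the week-12 tests in arms 1 and 3 are within it.

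The reply does not close the gap. None of these sections alters the definition, and 5.5.4 deals with serious events only. No comparable wording reaches the non-serious injuries that 5.7 expects. Counting the multivitamin as a pharmaceutical product would settle arms 2 and 4 after the first tablet, but would still leave out baseline testing.

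**Conclusion.** The point holds as a gap in scope. Events at baseline testing are outside the literal definition for all 72 women. Coverage in arms 2 and 4 (36 women) depends on an unstated classification of the multivitamin. Capture of exercise harms can therefore differ between arms 2 and 3 (18 women each). The practical weight falls on non-serious events and on baseline testing, since 5.5.4 and the schedule suggest that serious events would probably be reported wherever they arose.

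It would go too far to say that a planned safety comparison is biased. Section 7 contains no safety endpoint and no formal comparison of safety between arms. What suffers is the descriptive safety record that the pilot hands to the next study. The documents give no event rate for exercise injuries in this population, so the number of events that might be missed cannot be estimated from them.

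The conclusion rests on the visible text, on the ordinary meaning of the words in 5.5.3, and on the assumption that the redacted parts of 5.6.2 contain no adverse-event rule.

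**What to change.** 1. Move 5.5.3 and 5.5.4 into a section that applies to the whole trial.
2. Define an adverse event as any unfavourable medical event in any enrolled woman, in all four arms, from the first study procedure onward. State that enrolment here runs from consent, so that baseline testing is included. Align the definitions of serious and unexpected events with this.
3. Ask about adverse events on the same schedule in every arm, for example at the weekly calls, and word 5.5.2 and 5.6.2.3 to match.
4. Add an attribution field to the adverse-event form with four entries: calcitriol, multivitamin, exercise programme and study testing.

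The cost is protocol wording, one form field and a standard question at contacts that the schedule already appears to include for every arm. A modest number of additional minor musculoskeletal events would have to be recorded. Treatment, sample size and visits do not change.
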